2. OBJECTIVES, ENDPOINTS, AND HYPOTHESIS

2.1. Objectives and Endpoints

An overview of the objectives and endpoints is provided in [Table 1](#).

Table 1: Objectives and Endpoints

Objectives		Endpoints	
Primary			
1	To evaluate the VE of a heterologous vaccine regimen utilizing Ad26.Mos4.HIV and aluminum phosphate-adjuvanted Clade C gp140 and Mosaic gp140 for the prevention of HIV-1 infection in HIV-1 seronegative cis-gender men and transgender individuals having sex with cis-gender men and/or transgender individuals.	1	Confirmed HIV-1 infections diagnosed between Month 7 and Month x (with $24 \leq x \leq 30$) visits in the PP population.
Secondary			
1	To evaluate the safety and reactogenicity of a heterologous vaccine regimen utilizing Ad26.Mos4.HIV and aluminum phosphate-adjuvanted Clade C gp140 and Mosaic gp140 for the prevention of HIV-1 infection in HIV-1 seronegative cis-gender men and transgender individuals having sex with cis-gender men and/or transgender individuals.	1	
 Reactogenicity: Solicited administration site and systemic adverse events for 7 days after each vaccination Unsolicited adverse events for 28 days after each vaccination AESIs for 6 months after the last vaccination MAAEs for the entire duration of the study Serious adverse events for the entire duration of the study Discontinuations from the study or vaccination due to adverse events
2	To evaluate VE at other timepoints and in other analysis populations.	2	Confirmed HIV-1 infections over different time intervals (eg, VE[0-x months], VE[13-x months]) and in different populations (eg, mITT, mITT-2, mITT-3, FIS).
3	To evaluate VE by and adjusting for potential (baseline) confounders.	3	Potential confounders include but are not limited to: demographic characteristics, baseline Ad26 seropositivity status and titer, sexual risk behavior, and PrEP use.
Exploratory			
1	To evaluate whether VE differs by phenotypic characteristics of HIV, such as neutralization sensitivity, and whether there is evidence of vaccine-induced immune pressure on the viral phenotype.	1	Confirmed HIV-1 infection diagnosed after Day 1 through Month 30 and inferred transmitted viral isolate(s) phenotype(s) from HIV-1-infected mITT participants at the earliest available post-infection timepoint, and possible subsequent visits.

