9.4. Safety Evaluations

Details regarding the independent DSMB are provided in [Section 11.9](#).

Any clinically significant abnormalities that are considered related to vaccination persisting at the end of the study/early withdrawal will be followed by the investigator until resolution or until a clinically stable condition is reached (see Section 12.3.2).

All adverse events and laboratory data will be graded for severity according to the criteria presented in Section 12.1.3.

Adverse Events

All serious adverse events and adverse events and special reporting situations, that are related to study procedures or that are related to non-investigational concomitant sponsor products will be reported from the time a signed and dated ICF is obtained until the end of the study/early withdrawal. Clinically relevant medical events not meeting the above criteria and occurring between signing of ICF and the moment of first vaccination will be collected on the Medical History CRF page as pre-existing conditions.

Solicited adverse events, collected through a diary, will be recorded daily for each vaccination from the moment of vaccination until 7 days post-vaccination.

All other unsolicited adverse events and special reporting situations will be reported for each vaccination from the moment of vaccination until 28 days post-vaccination. Unsolicited adverse events with the onset date outside the timeframe defined above (>28 days after previous study vaccination), which are ongoing on the day of the subsequent vaccination, should be recorded as such.

From the time of local approval of protocol amendment 5 onwards, TTS is considered to be an AESI (see Section 12.3.4). Thrombotic events and/or thrombocytopenia (defined as platelet count below the LLN range for the testing lab) are considered to be potential AESIs. All AESIs, including potential AESIs, will be reported to the sponsor from the moment of first vaccination until 6 months after the last vaccination. Each potential AESI will be reviewed to identify a TTS case.

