All serious adverse events, MAAEs, and adverse events leading to discontinuation (regardless of causal relationship) are to be reported from the moment of first vaccination for the duration of the study, which may include contact for safety follow-up. The HPX3002/HVTN 706 safety review team will review the safety information during the conduct of the study. The sponsor will evaluate any safety information that is spontaneously reported by an investigator beyond the time frame specified in the protocol.

All AEs will be followed until resolution or until clinically stable.

Medically-attended adverse events (MAAEs) are defined as adverse events with medically attended visits including hospital, emergency room, urgent care clinic, or other visits to or from medical personnel for any reason. Potentially immune-mediated medical conditions (PIMMCs) and new onset of chronic diseases will be collected as part of the MAAEs. Adverse events identified during a routine study visit will not be considered MAAEs. STIs (including HIV-2 infection) are associated with an increased likelihood to acquire HIV infection. Note that

an STI identified from study visit testing, for which a participant receives subsequent medical intervention, fulfils the criteria of an MAAE.

Based on regulatory feedback, special attention will be put on PIMMC that are reported as MAAEs. These events will be collected and analyzed. A list of PIMMCs defined for this study is presented in [Attachment 3](#).

For solicited adverse events, the following applies.

Solicited Adverse Events

Solicited adverse events are used to assess the reactogenicity of the study vaccine and are predefined local (at the administration site) and systemic events for which the participant is specifically questioned, and which are noted by participants in their diary.

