11.6.2. Unsolicited Adverse Events, AESIs, MAAEs and Serious Adverse Events

The verbatim terms used in the CRF by investigators to identify adverse events will be coded using the Medical Dictionary for Regulatory Activities (MedDRA). Tables will show, by vaccination group, the number and percentage of participants experiencing an adverse event within a system organ class or within a preferred term category by severity and by relationship to study vaccine. All reported adverse events and events-related diary information with onset or worsening within 28 days after each vaccination (ie, treatment-emergent adverse events) will be included in the analysis. For each adverse event, the percentage of participants who experience at least 1 occurrence of the given event will be summarized by vaccine group. A participant with multiple adverse events within a category will be counted once under the maximum severity and by causal relationship to study vaccine. Formal statistical testing comparing groups is not planned since interpretation of differences must rely heavily upon clinical judgement. Parallel analyses will include all AESIs, serious adverse events and adverse events leading to participant withdrawal or early discontinuation of study vaccine(s).

For this study events of interest are PIMMCs. PIMMCs that are recorded as MAAEs will be collected and analyzed.

Summaries, listings, datasets, or participant narratives may be provided, as appropriate, for those participants who die, who discontinue treatment due to an adverse event, or who experience a serious adverse event or an AESI.

Summaries and listings may be provided separately for adverse events with onset outside the above defined timeframe and that were reported pre-dose at the moment of subsequent vaccinations.

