12. ADVERSE EVENT REPORTING

Timely, accurate, and complete reporting and analysis of safety information from clinical studies are crucial for the protection of participants, investigators, and the sponsor, and are mandated by regulatory agencies worldwide. The sponsor has established Standard Operating Procedures in

conformity with regulatory requirements worldwide to ensure appropriate reporting of safety information; all clinical studies conducted by the sponsor or its affiliates will be conducted in accordance with those procedures.

Method of Detecting Adverse Events, AESIs, MAAEs and Serious Adverse Events

Care will be taken not to introduce bias when detecting adverse events, AESIs, MAAEs or serious adverse events. Open-ended and nonleading verbal questioning of the participant is the preferred method to inquire about adverse event occurrence.

Solicited Adverse Events

Solicited adverse events are predefined administration site and systemic events for which participants are specifically questioned and which are noted in their diary (see Section 9.1.1).

Unsolicited Adverse Events

Unsolicited adverse events are all adverse events for which the participant is specifically not questioned in the participant diary.

AESIs

For details, see Section 12.3.4.

Medically-attended Adverse Events

Medically-attended adverse events (MAAEs) are adverse events with medically attended visits including hospital, emergency room, urgent care clinic, or other visits to or from medical personnel for any reason.

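### Read literally, the MAAE rules leave a non-serious PIMMC first identified at a scheduled visit out of the PIMMC analysis, and Protocol 9.4, 11.6.2 and 12 need reconciling

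*Protocol*

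**What the plan says.** Protocol 9.4 makes the MAAE category the collection route for these conditions: "Potentially immune-mediated medical conditions (PIMMCs) and new onset of chronic diseases will be collected as part of the MAAEs". The next sentence removes a class of events from that category: "Adverse events identified during a routine study visit will not be considered MAAEs". Further on, 9.4 says that "special attention will be put on PIMMC that are reported as MAAEs".

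Protocol 11.6.2 names PIMMCs as the events of interest and says "PIMMCs that are recorded as MAAEs will be collected and analyzed". It gives no other route into a PIMMC analysis.

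Protocol 12 defines MAAEs again. It ends on "other visits to or from medical personnel for any reason" and has no exclusion for routine study visits.

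One type of event has an explicit clarification in 9.4: "an STI identified from study visit testing, for which a participant receives subsequent medical intervention, fulfils the criteria of an MAAE". Nothing equivalent is written for PIMMCs or new-onset chronic disease.

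Protocol Table 1 (Section 2.1) lists as a secondary safety endpoint "MAAEs for the entire duration of the study". PIMMCs do not appear in that table. SAP Section 4 repeats the MAAE endpoint, but SAP 4.1 lists no MAAE or PIMMC table, and the SAP does not mention PIMMCs at all.

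**The concern.** The amendment log gives the reason for adding MAAE recording (Amendment 1): health authorities asked for it, and it was meant to pick up PIMMCs and new-onset chronic disease. The exclusion in 9.4 turns on where an event was identified; the definition in Section 12 turns on whether it was medically attended. The same new vitiligo, psoriasis or facial palsy (all covered by Attachment 3) could therefore count as an event of interest if a participant's own doctor saw it first, and not if the study clinician did. Two sites could also classify one event differently, depending on which section they follow.

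At stake is how completely late-onset, non-serious immune-mediated conditions are counted in the one analysis set aside for them.

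**Working it through.** No stated figure depends on this point, so there is none to reproduce. The check is whether any other rule brings such an event back in.

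**Step 1: the event.** Take a condition listed in Attachment 3 that is non-serious, does not lead to discontinuation, is not a thrombotic event or thrombocytopenia, is first identified at a scheduled visit, and has no later medically attended visit. By the 9.4 exclusion it is not an MAAE. By 11.6.2 it is then not in the PIMMC analysis.

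**Step 2: the unsolicited-event window.** Protocol 9.4: "All other unsolicited adverse events and special reporting situations will be reported for each vaccination from the moment of vaccination until 28 days post-vaccination".

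- Four vaccinations × 28 days = 112 days. The Month 30 target day is 910, and 112/910 = 12.3%.
- Counting the vaccination day as well: 4 × 29 = 116, and 116/910 = 12.7%.
- So about 87% to 88% of scheduled days to Month 30 lie outside a window.

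Target vaccination days are 1, 84, 168 and 364 (Protocol 9.1.2). Days from the preceding target vaccination to each visit:

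| Visit | Target day | Days since preceding dose |
|---|---|---|
| Month 3 | 84 | 83 |
| Month 6 | 168 | 84 |
| Month 7 | 196 | 28 |
| Month 9 | 273 | 105 |
| Month 12 | 364 | 196 |
| Month 13 | 394 | 30 |
| Month 15 | 455 | 91 |
| Month 18 | 546 | 182 |
| Month 21 | 637 | 273 |
| Month 24 | 728 | 364 |
| Month 27 | 819 | 455 |
| Month 30 | 910 | 546 |

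Only Month 7 falls within 28 days by target day. Actual visit days move within their windows, and onset date rather than visit date decides, so Months 7 and 13 can go either way. An event that does qualify is tabulated as an unsolicited event; that does not make it an MAAE.

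**Step 3: events ongoing at the next vaccination.** Protocol 9.4 has these recorded even when onset is beyond 28 days. This works only while another vaccination is due, so it ends at Month 12.

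**Step 4: what the later visits collect.** For Visits 9 to 14, Protocol 9.1.5 lists serious events, MAAEs, events leading to study discontinuation, and events of special interest up to Visit 10. Section 9.1.6 is similar after Month 30, without the events of special interest. The Step 1 event fits none of these.

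**Step 5: examination findings.** Protocol 11.6.3 has clinically relevant examination findings reported and tabulated as adverse events, with no time limit stated there. This is the one remaining route after Month 12 for an event outside the windows. It leads to an adverse event record, not to an MAAE or the PIMMC analysis.

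**Result.** No route found in the documents returns the Step 1 event to the PIMMC/MAAE analysis. Some routes keep it in the safety database.

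**The case against.** The best defence is that the exclusion is only loosely drafted. The sentence before it specifically says that PIMMCs are collected as MAAEs, and a specific instruction can be read as prevailing over a general one. On that view the exclusion means only that a routine study visit is not itself the medical attendance. Section 12 supports this, since it has no exclusion. So does the Amendment 7 rationale for the sexually transmitted infection note: once follow-up takes place, the event meets the MAAE criteria. The same logic would cover a PIMMC seen at a study visit and then referred or treated. Many Attachment 3 conditions, such as Crohn disease or multiple sclerosis, would hardly be diagnosed at a study visit without further care, and no routine safety laboratory samples are drawn.

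Much of this stands, and it is why the gap is limited to events with no later medical attendance. It does not remove the gap: the text states the follow-up logic only for sexually transmitted infections, and a site applying 9.4 literally would be following the protocol.

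Five stronger readings are tempting, and the documents do not support them:

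- A reader might infer that a study endpoint loses events because PIMMCs drop out of it. PIMMCs are declared events of interest, not a Table 1 endpoint.
- A reader might infer that the event need not be recorded at all. Section 11.6.3 says otherwise for clinically relevant examination findings.
- A reader might take 87% to 88% as the share of PIMMCs at risk of being missed. It is a share of calendar days; the documents give neither a PIMMC rate nor the fraction first noticed at study visits without later care.
- A reader might suppose that every scheduled visit examines every participant fully. For uninfected participants the only scheduled full examination after baseline is at Month 30; the others are targeted and symptom-directed.
- A reader might infer a biased comparison between arms. The rule is identical in both blinded arms and the safety analysis is descriptive.

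**Conclusion.** The point holds as a contradiction between definitions with a limited consequence. Protocol 9.4, 11.6.2 and 12 do not agree on what an MAAE is. Followed literally, 9.4 and 11.6.2 omit from the events-of-interest analysis a non-serious PIMMC first identified at a scheduled visit and never medically attended afterwards. After Month 12, and outside the 28-day windows, such an event has one recording route, through Section 11.6.3, and that route does not lead to the PIMMC analysis.

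The supported harm is reduced sensitivity in both arms, of unknown size. The conclusion assumes that sites apply the exclusion as written. If they read it as concerning attendance only, the loss is smaller, but classification may then vary between sites. The absence of MAAE and PIMMC tables is a statement about the SAP text; the separate Data Presentation Specifications, which hold the mock tables, were not available and might list them.

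**What to change.** 1. **Recording.** Reconcile Protocol 9.4, 11.6.2 and 12 under one MAAE definition, and state that an Attachment 3 condition or new-onset chronic disease first identified at a study visit is recorded for the whole study.
2. **Analysis.** In Protocol 11.6.2 and SAP 4.1, build the PIMMC table from all recorded adverse events, serious adverse events and MAAEs that match a fixed MedDRA term list based on Attachment 3, whatever their MAAE flag. List MAAE and PIMMC tables explicitly in SAP 4.1.

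The recording change costs a few sentences and slightly more site entries. The analysis change needs a term search over data already held, but the term list must be defined first, because Attachment 3 says it may not be exhaustive. The SAP amendment history dates study-level unblinding to 18 January 2023, so the recording change can now do little for visits already completed, while the analysis change remains fully feasible. The term list should be dated and reported as set after unblinding.

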9.5. Participant Reported Outcomes

Social impact, sexual activity, absenteeism, vaccination regimen acceptance, and PrEP use will be evaluated over the study period, until the end of follow up, through questionnaires completed under

confidentiality by the study participants. Replies to questionnaires will be assessed in the following groups:

1. In vaccine and placebo recipients,
2. In participants who become HIV-1 infected in comparison to non-infected participants,
3. In VISP positive and negative study participants,
4. In participants who are using PrEP or not during the course of the study, if applicable.

For the full questionnaires, refer to the Study Specific Procedures Binder.

9.5.1. Social Impact Measured Using Questionnaire

Participants in prophylactic HIV-vaccine clinical studies may experience problems with personal relationships, employment, education, health care, housing, health, disability or life insurance, travel, and immigration.¹ In relation to a participant's family, friends, and/or colleagues, the social impact could manifest in one or more ways, resulting in social conflicts and stigmatization, for example:

1. The investigational vaccine is thought to be harmful to the participant's health, including a belief that it might cause HIV infection.
2. The participant is perceived as HIV-infected or at high risk.
3. Repercussions from VISP.

For these reasons, participants will complete a social impact questionnaire at the time points specified in the [Time and Events Schedule](#), to evaluate any potential consequences of the participant's enrollment in the study.

9.5.2. Sexual Activity Questionnaire

In order to collect information to assess the level of risk of HIV infection throughout the study, participants will complete a sexual activity questionnaire, at the time points specified in the [Time and Events Schedule](#). The recall period for this questionnaire is the last month.

9.5.3. Questionnaire on the Use of PrEP

Information with regard to the use of and, if applicable, adherence to PrEP will be collected for all participants by means of a questionnaire. The questionnaire will be completed at the time points specified in the [Time and Events Schedule](#).

9.5.4. Other Participant Reported Outcomes

At each visit (except for Visit 2a and Visit 3a), participants will be questioned on their level of absenteeism, defined as health-related productivity loss due to sick-leave, since their last visit at which absenteeism was recorded.

In addition, at Visit 8, 1 month post-vaccination 4, participants will be asked how they perceived their experience with this HIV vaccination.

9.6. Sample Collection and Handling

The actual dates and time of sample collection must be recorded in the laboratory requisition form.

Refer to the [Time and Events Schedule](#) for the timing and frequency of all sample collections.

Instructions for the collection, handling, storage, and shipment of samples are found in the Study-Specific Procedures Binder that will be provided. Collection, handling, storage, and shipment of samples must be under the specified, and where applicable, controlled temperature conditions as indicated in the Study-Specific Procedures Binder.

10. PARTICIPANT COMPLETION/DISCONTINUATION OF STUDY VACCINATION/ WITHDRAWAL FROM THE STUDY

10.1. Completion

The study will be considered completed when the last participant completed the Month 30 visit or discontinued earlier. Participants will continue the study until the last participant has completed the Month 30 visit or discontinued earlier.

At the end of the study, participants may be offered the possibility to enter a follow-up phase or program.

10.2. Discontinuation of Study Vaccination/Withdrawal from the Study

Discontinuation of Study Vaccination

Participants will be withdrawn from study vaccine administration for the reasons listed below. These participants must not receive any additional dose of study vaccine but should continue the visit schedule as planned with assessments per the [Time and Event Schedule](#) including assessments of safety and HIV diagnosis. Participants who received the first 3 vaccinations but discontinue study vaccination before receiving the 4th vaccination, should continue the visit schedule as planned with assessments per the [Time and Event Schedule](#) including assessments of safety, immunogenicity and HIV diagnosis. Additional unscheduled visits may be performed for safety/reactogenicity reasons, if needed. In case of questions, the investigator is encouraged to contact the HPX3002/HVTN 706 safety review team.

- Unblinding due to safety reasons
- Pregnancy
- Confirmed HIV-1 or HIV-2 infection
- Any related adverse event, worsening of health status or intercurrent illnesses that, in the opinion of the investigator, required discontinuation from study vaccine
- Anaphylactic reaction following vaccination
- Serious adverse event or other potentially life-threatening (Grade 4) event that is determined to be related to study vaccine

- Chronic or recurrent use of systemic immunomodulators/suppressants, eg, cancer chemotherapeutic agents (after discussion with the HPX3002/HVTN 706 safety review team)
- Use of HIV-related mAbs
- From the time of local approval of protocol amendment 5 onwards: participant previously experienced TTS or HITT.

Withdrawal From the Study

Each participant has the right to withdraw from the study at any time for any reason without affecting the right to treatment by the investigator. The investigator should make an attempt to contact participants who did not return for scheduled visits or follow-up. Although the participant is not obliged to give reason(s) for withdrawing prematurely, the investigator should make a reasonable effort to ascertain the reason(s) while fully respecting the participant's rights.

A participant will be withdrawn from the study for any of the following reasons:

- Lost to follow-up
- Withdrawal of consent
- Death
- Repeated failure to comply with protocol requirements
- Decision by the sponsor or the investigator to stop or cancel the study
- Decision by local regulatory authorities or IRB/IEC to stop or cancel the study

If a participant is lost to follow-up, every reasonable effort must be made by the study-site personnel to contact the participant and determine the reason for discontinuation/withdrawal. The measures taken to follow-up must be documented.

When a participant withdraws before completing the study, the reason for withdrawal is to be documented in the CRF and in the source document. Study vaccine assigned to the withdrawn participant may not be assigned to another participant. Participants who are vaccinated and withdraw will not be replaced. If a participant withdraws early from the study, assessments for early withdrawal should be obtained (see Section 9.1.8).

Participants who wish to withdraw consent from participation in the study will be offered a single exit visit for safety follow-up (prior to formal withdrawal of consent). They have the right to refuse.

